2. STUDY AIMS

AIM 1: Adapt and refine the SMART Couples intervention and identify augmentative intervention strategies guided by the collaborative intervention planning framework⁴⁰ to create an integrated, couple-based ART adherence intervention for HIV+ PWID and their treatment support partners.

AIM 2: Pilot test the resulting couple-based intervention among 66 heterosexual PWID couples in Kazakhstan through a randomized control trial (RCT) to assess the safety, feasibility and acceptability of the intervention and obtain preliminary estimates of adherence outcomes (e.g. electronic monitoring devices, self-reported adherence, viral load) in the intervention arm versus standard of care.

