4.4. Inclusion/Exclusion Criteria

Participant inclusion criteria

We will recruit 66 dyads (n=132) to participate in a randomized control trial of the adapted couple-based intervention. We anticipate we will need to screen 450 individuals to obtain 66 eligible dyads (n=132). Dyads are eligible to participate if

- (1) both partners are ≥ 18 years old,
- (2) both identify each other as their intimate partner, family member, friend, or other person within their social network,

- (3) the relationship has existed at least 3 months,
- (4) both report feeling safe participating with their partner in the study,
- (5) neither reports any severe physical or sexual violence perpetrated by the other partner in the past year,
- (6) both are able to provide informed consent and follow study procedures, and
- (7) both are fluent in Russian.

In addition, the “index case” (partner initially recruited from AIDS Center) must

- (1) be confirmed HIV+ by the AIDS Center,
- (2) have been on ART at least 3 months,
- (3) not be virally suppressed according to the AIDS Center standard (<500 copies/ml), and
- (4) report injecting any drug in the past year.

“Partners” may be HIV- or HIV+ and may or may not be a PWID. Because dyad dynamics may depend on the sex of the “index case”, women will be the “index case” in at least a third of dyads. If both partners meet eligibility criteria, both will provide consent, complete the baseline assessment, and be randomized to study arm.

Participant exclusion criteria

Individuals who do not meet inclusion criteria or who meet any of the following criteria will be excluded from the study.

- (1) unable to provide informed consent,
- (2) unwilling or unable to participate in study procedures,
- (3) any condition that, in the opinion of the principal investigator and research staff, would make participation in the study unsafe, complicate interpretation of study outcome data, or otherwise interfere with achieving the study objectives.

4.5. Study Enrollment. The Baseline Visit will be conducted remotely by phone or computer with participants. At the Baseline Visit, the participants will provide informed consent, be enrolled in the study, complete the baseline assessment through Qualtrics, and self-collect urine and hair samples (if HIV-positive), which will then be mailed to the GHRCCA research staff.

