4.6.3. Immediately Post-Intervention (IPI) Visit (for all participants)

The IPI will be conducted by phone/video call or in-person in GHRCCA’s field office (post-COVID). Prior to the visit, an RA will mail an IPI kit to participants containing materials to self-collect hair and urine samples. For in-person visits, participants will self-collect samples at the GHRCCA field office. The following procedures/assessments will be performed at the IPI visit:

1. The RA will verify the participants by the name on the record and update the **Locator Information Form**;
2. The RA will send the **IPI Assessment** through Qualtrics;
3. The RA will conduct an **EMD** test and will check in with the participant regarding EMD uses and resolve any issues;
4. Participants will self-collect urine samples and hair samples to measure biological levels of medication adherence. These samples will be mailed to GHRCCA staff.
5. At the participant’s next regular AIDS Center visit, the nurse will obtain an additional **blood sample** to conduct dried blood spot sampling and measure levels of medication in the body

4.6.4. 3-month and 6-month Follow-Up Visits (for all participants)

Three- and six-month Follow-Up Visits will be conducted by phone/video call or in-person in GHRCCA’s field office (post-COVID). The following procedures/assessments will be performed at the 3- and 6-month follow-up visits:

1. The RA will verify the participants by the name on the record and update the **Locator Information Form**;
2. The RA will send the **3- or 6-month follow-up assessment** through Qualtrics;
3. At the **3-month** follow-up, the RA will conduct an **EMD** test and will check in with the participant regarding EMD uses and resolve any issues. At the **6-month** follow-up, the participant will mail the **EMD** back to the RA.
4. After the **6-month** follow-up, the RA will administer the Exit Interview;

4.6.5. Pilot study assessments. Participants in both arms will receive the same schedule of assessments. There will be four main repeated assessment occasions: baseline “pre-intervention”, immediately post-intervention (IPI), 3-month and 6-month follow-up. The primary adherence outcome will be proportion of prescribed doses taken as measured by EMD. Study assessments will be delivered remotely through Qualtrics.

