4.6.11. Safety, Acceptability, Feasibility, Retention and Implementation Data. Intervention safety will be assessed through adverse event reporting by study and clinic staff and an exit interview asking about any negative experiences during the intervention. We will assess acceptability and feasibility of the adapted intervention and biological testing. Both partners will be assessed at the end of each intervention session on satisfaction and obstacles to participation. A brief survey will ask about participants' experiences with biological sample collection. We will track the number of participants retained in the study. For those who drop out, we will attempt to contact them to determine the reason. Staff will be asked questions about intervention delivery, specimen collection and challenges and facilitators of implementation.

4.6.12. Sample size and power considerations for the pilot RCT. We can estimate power for this study based on previous studies.^{33,35} Based on Project Renaissance attrition rates,³³ we anticipate there will be no more than 10% attrition throughout the study. Power analyses were conducted with G*Power⁴⁹ (v3.1.0) using a repeated measures within-between ANOVA approach and $\alpha=.05$. With 30 dyads per arm, we would have 80% power to detect a medium effect size ($f=.15$). Thus, we will recruit 66 couples and aim to have 60 for analysis.

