6.4. Adverse Events

Serious adverse events include death, a life-threatening event, or an event resulting in hospitalization, prolongation of hospitalization, and disability. Serious adverse events, regardless of whether or not they are study-related, will be reported to the Columbia University IRB and the IRB at the study site serving the participant. Other adverse events include breaches of confidentiality (both intentional – e.g., mandated reporting of suicidal/homicidal participants – and unintentional), and non-life threatening psychological distress, arrest by the police and violence. The PI and research staff will closely monitor adverse events. The research team is aware that the study sample is likely to experience some adverse events, though unlikely to be study-related, due to their status in Kazakhstani society, their current or past history of law-breaking activity (e.g., use of or selling of illegal drugs), and the high levels of service needs. Drawing upon past GHRCCA studies, the research team designed an adverse event form.

Study staff will identify, manage and document all adverse events. These events may be identified by RAs, the Project Manager, or other staff, or they may be reported by participants. The procedures used to track, report, and examine adverse events are described below.

- 1) After an adverse event is reported/detected, the study staff member who identified the event will complete an Adverse Event Report form. The report form will include the date, description of the event, duration, severity, measures taken to ameliorate the adverse event, and disposition-related information (e.g., time spent providing referrals and type of referral). The report form will be reviewed and signed by the project manager, [name], and [name], who will be responsible for ensuring that appropriate actions have been taken.
- 2) Drs. [name] and [name] will consult with the Project Manager and any involved staff to ascertain whether the event was related to participation in the study and to ensure that an adequate response is provided to the participant. This will be followed by submission of a report to the IRBs at Columbia University and the Al-Farabi Kazakh National University.

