## 1. INTRODUCTION

The SMART Couple II study was designed to adapt a couples-based antiretroviral therapy (ART) adherence intervention for HIV-positive people who inject drugs (PWID) in Kazakhstan and their treatment support partners. The adapted intervention was then pilot tested among 66 HIV-positive PWID and their treatment support partners (n=66) to assess the feasibility and acceptability of the intervention and obtain preliminary estimates of adherence outcomes in the intervention arm versus the standard of care arm.

This document outlines the statistical analysis plan that will be followed to assess the adherence outcomes.

**Primary Outcome:** To evaluate the difference in ART adherence as measured through an electronic monitoring device (EMD) throughout the six-month follow-up between the intervention and standard of care arms.

**Secondary Outcome 1:** To evaluate the difference in biological measures of ART adherence (e.g., viral load, hair samples, dried blood spot testing) between the intervention and standard of care arms.

**Secondary Outcome 2:** To evaluate the difference in self-reported ART adherence as measured through a validated three-item adherence scale at the six-month follow-up between the intervention and standard of care arms.

**Secondary Outcome 3:** To evaluate the difference in uptake of opioid substitution therapy (OST) at the six-month follow-up between the intervention and standard of care arms.

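### Safety is part of Aim 2, but no adverse-event question on a common schedule in both arms is described, and no safety summary is specified

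*Protocol*

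**What the plan says.** Protocol section 2 (Aim 2) runs the pilot "to assess the safety, feasibility and acceptability of the intervention", and section 4.7 puts safety first among the purposes of a pilot.

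Section 4.6.11 names two sources of safety data: "adverse event reporting by study and clinic staff", and "an exit interview asking about any negative experiences during the intervention". On how events come to light, section 6.4 says: "These events may be identified by RAs, the Project Manager, or other staff, or they may be reported by participants".

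Section 4.6.4 places the exit interview after the 6-month follow-up, where "the RA will administer the Exit Interview"; the visit list is headed as applying to all participants. The procedure lists for baseline, sessions, IPI and follow-up (4.6.1 to 4.6.4) contain no adverse-event item, and the weekly app topics (4.6.7) do not include one. One entry condition in section 4.4 is that "both report feeling safe participating with their partner in the study"; another rules out severe partner violence in the past year. No repeat of either is described, although section 6.4 counts violence as an adverse event.

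The SAP introduction gives the purpose of the pilot as "to assess the feasibility and acceptability of the intervention and obtain preliminary estimates of adherence outcomes". It lists no safety outcome or analysis.

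**The concern.** A safety aim needs events collected in a way that does not depend on arm, on memory or on staying in the study. As described, an event is recorded if someone notices it or mentions it, and the intervention arm has more occasions for that. The one described direct question on negative experiences comes late, is described as being about the intervention, and mainly reaches completers.

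The protocol itself expects background events in this population. More contact in one arm could make the intervention look less safe than it is. Late questioning of completers could make it look safer. The pilot is meant to inform a full-scale trial, so an event count that cannot be read clearly is a real loss. A low count could mean few events or few questions.

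**Working it through.** No stated safety figure exists to reproduce. The check compares schedules, timing and reach.

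**1. Scheduled contacts by arm.** Inputs: four assessments in both arms (4.6.5), three facilitator sessions in the intervention arm (4.6, 4.6.2), and standard of care with nurse appointments at baseline, 3 and 6 months (4.6). The documents do not say whether intervention dyads keep those nurse appointments. Randomisation takes place at the baseline visit (4.6.1), so that visit cannot reveal a later event. Both counts are shown.

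| Assumption on nurse visits | SOC v intervention, baseline counted | SOC v intervention, baseline excluded |
|---|---|---|
| Not counted | 4 v 4+3 = 7 | 3 v 3+3 = 6 |
| Both arms keep them | 4+3 = 7 v 7+3 = 10 | 3+2 = 5 v 6+2 = 8 |
| SOC only | 4+3 = 7 v 7 | 3+2 = 5 v 6 |

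The excess is three contacts in the first two rows, and zero or one in the third. Device calls (4.6.6) and the weekly app (4.6.7) add contact in both arms and shrink the relative difference.

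**2. Delay to the exit interview.** Sessions are expected to take one month and must end within two months of the first (4.6, 4.6.2). Assume that the first session is close to baseline.
- Months counted from baseline (SAP 3.2.1 and 4.2: IPI at 1 month, outcome over 0 to 180 days): 6 − 1 = 5 or 6 − 2 = 4 months after the last session, and up to 6 after the first.
- Months counted after the intervention (protocol 4.2): at least 6 months after the last session, and 6 + 1 = 7 to 6 + 2 = 8 after the first.

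**3. Who is missed.** Protocol 4.6.12 allows up to 10% attrition and aims for 60 of 66 dyads: 66 × 0.10 = 6.6, and 66 − 60 = 6. So 6 or 7 dyads would not reach the exit interview, about 3 per arm if losses are even. Let pc and pd be the proportions with a negative experience among completers and dropouts. The true proportion is 0.9·pc + 0.1·pd, so using completers alone is wrong by 0.1·(pd − pc). At 10% attrition that is at most 10 percentage points. It would be more in one arm if losses concentrate there. Neither pc nor pd is given.

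**4. Precision.** Even with complete capture, 0 events in 33 intervention dyads has a two-sided exact 95% upper limit of 1 − 0.025^(1/33) = 10.6%. With 30 dyads it is 11.6%. A by-arm table would show this.

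**5. Where safety is analysed.** Protocol 4.7 plans means and proportions with 95% confidence intervals, but its examples are all adherence measures. The five data sources in section 5 include neither adverse-event forms nor the exit interview. The SAP confines itself to adherence outcomes and OST uptake.

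**The case against.** The protocol has more safeguards than its two named sources suggest. Participants can report events themselves. "Serious adverse events, regardless of whether or not they are study-related, will be reported to the Columbia University IRB", so serious events do not depend on a judgement of relatedness. All event data are reviewed every two months, and withdrawals due to an event are monitored (6.4). Both partners are assessed after each session on satisfaction and obstacles, and staff try to learn why dropouts left (4.6.11). These reduce the problem. None is a common question: the review sees only what was captured, the session assessments are in one arm and do not ask about adverse events, and the dropout contact is an attempt to learn a reason.

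A reader might infer more than the documents support:

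- *That no visit asks about adverse events.* The Qualtrics content is not reproduced, and the SAP says that the surveys cover many topics. Only the absence of a described question can be stated. The exit-interview text is not given either, so one cannot say that it is meaningless in standard of care.
- *That the safety data are biased by a calculable amount.* Any chance of detection per contact would be invented, and the contact excess depends on the unstated nurse visits.
- *That no conclusion on safety would be possible.* No between-arm safety test is planned, and a descriptive pilot that reviews each event can still say something useful.
- *That the SAP abandons the safety aim.* It states that its scope is adherence outcomes. What stands is that its summary of the purpose omits safety and that neither document supplies the missing summary.

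**Conclusion.** The point holds in a limited form. Safety is an aim, yet adverse-event capture is described as unsolicited. The intervention arm has three more staff sessions, and the one described direct question on negative experiences comes about 4 to 6 months or more after the last session, mainly to completers. The data are open to detection bias, recall bias and dropout bias. The first could make the intervention look less safe and the last could make it look safer; neither size is known.

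This rests on two assumptions: that the unreproduced surveys contain no common adverse-event item, and that intervention dyads keep their usual nurse visits. If the second fails, the contact excess falls to zero or one, but the timing, reach and reporting gaps remain. The change is worth making because an identical question in surveys already scheduled is cheap and clearly better than the described method.

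**What to change.** **Protocol 4.6.3, 4.6.4 and 4.6.11.** Add a short identical checklist to the IPI, 3-month and 6-month surveys in both arms, answered privately by each partner about the time since the last survey. It should cover the events named in section 6.4 (hospitalisation, distress, arrest, violence, confidentiality breach) and repeat the two entry questions on feeling safe and on partner violence. Ask the negative-experiences question at IPI as well as at exit, and in the contact with dropouts. If the surveys already contain such items, say so and name them as a safety source.

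**Analysis plan.** Name safety in the purpose. Report by arm the proportion of dyads with at least one checklist event, with a 95% confidence interval. List spontaneously reported and session-detected events separately.

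**Cost.** A few survey items and one table. The survey becomes slightly longer and the recorded event count will rise. Violence items in a remote survey need private completion, because the partner may be present.

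**If collection is complete.** The SAP describes the trial in the past tense and reports scale reliability in this sample, so new survey items may no longer be possible. The by-arm table of recorded events, split by detection route, can still be produced, and the checklist should carry to the planned full-scale trial.

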In the pilot testing phase, 66 HIV+ PWID and their treatment support partners (n=66) will participate in a pilot randomized controlled trial (RCT) of the adapted couple-based intervention developed in the pre-trial phase of the study. Psychologists and intervention facilitators will be trained to deliver the adapted intervention remotely to assess safety, feasibility, acceptability, retention, and preliminary estimates of adherence to directly inform a future, full-scale R01 efficacy trial. Couples will be randomized to the intervention or standard of care (SOC) arms and assessed with repeated measures at four time-points on ART adherence, behavioral outcomes (i.e., drug use, sexual risk behavior), social support processes, and biological measures from baseline to 6 months post-intervention (see **Table 2** below). Electronic monitoring device (EMD) and weekly mobile app data will be collected throughout the intervention and follow-up periods. Due to COVID-19, all study procedures will be conducted remotely.

4.3. Study location and Recruitment Sites. HIV+ PWID will be recruited from the Almaty AIDS Center, which has 1,546 patients on ART, 660 of whom are PWID prescribed ART at least 6 months, 240 of whom are not virally suppressed.⁴⁶ Current AIDS Center patients on ART are 57.6% male and 42.4% female.⁴⁶ The AIDS Center does not currently provide any routine adherence intervention to patients, but recognizes ART adherence as a significant problem and is highly motivated to conduct research and intervention adaptation with us.

4.3.1. Recruitment and Eligibility Screening. Participants will be recruited from the Almaty City AIDS Center. An epidemiologist at the Almaty City AIDS center will review patient records to determine which patients potentially meet eligibility requirements. A list of potentially eligible patients will be given to nurses at the Almaty City AIDS Center. Nurses will call patients to inform them about the study and, for those who are interested, conduct eligibility screening with them. The nurse will obtain consent from eligible participants to be contacted by research staff and provide research staff with the contact information of eligible participants who have consented to be contacted.

[figure not shown]

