4.6. STUDY PROCEDURES

We will conduct an RCT pilot trial of the adapted couple-based intervention. 66 couples will be randomized into two arms – 33 couples into the intervention arm and 33 couples into standard of care (SOC). SOC consists of an appointment with an AIDS Center nurse at baseline and three and six months later. Under current SOC in Almaty, no behavioral intervention is provided. Participants obtain prescription refills and give blood for viral load and CD4 tests once every 6 months. Participants receive viral load and CD4 test results only by request, and adherence is generally not assessed. We anticipate the intervention will consist of 3 sessions over the course of one month. Participants in both arms will be assessed at 4 time points: baseline “pre-intervention”, immediately post-intervention (IPI), 3-month follow-up, and 6-month follow-up. **Figure 2** illustrates participant flow through the study.

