#### 4.2. Dependent Variables

The dependent variables in this analysis are:

1. EMD measured ART adherence – Number of days EMD is opened from baseline to six-month follow-up (0 to 180 days) among participants in each arm.
2. Biological measures of ART adherence – Number of participants in each arm who are virally suppressed and adherent as measured through biological testing.
3. Self-reported ART adherence – Assessed by a validated three-item ART adherence scale. The three items are: 1) *Days taken* -- number of days the patient missed at least one dose of their medication (number of days, 0-30); 2) *Frequency* -- how often the patient took their medication in the way they were supposed to in the past 30 days (never/rarely/sometimes/usually/almost always/always); and 3) *Rating* – how good a job the patient did in taking their medication in the way they were supposed to in the past 30 days (very poor/poor/fair/good/very good/excellent). Responses were then linearly transformed into a scale of 0 to 100 (higher scores indicate greater adherence). The average score across the three items was calculated to represent overall adherence. Scale reliability among this sample was high (Cronbach's  $\alpha = .90$ ).
4. Uptake of OST – Number of participants who reported they were currently taking OST at the six-month follow-up.

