#### 4.5. Statistical Analysis Methods

Descriptive statistics of key independent variables and covariates will be summarized within each arm using frequencies or means (standard deviations) as appropriate. Overall participation rates will be reported in each arm based on the proportion of baseline participants who completed the six-month follow-up assessment.

To test **hypothesis 1 (H1)**, we will conduct t-tests to assess for differences in ART adherence rates over six months (0 to 180 days) between study arms.

To test **hypothesis 2 (H2)**, we will conduct chi-square tests to assess for differences in biological measures of ART adherence between study arms. Adjustments for small sample sizes will be made as appropriate.

To test **hypothesis 3 (H3)**, we will conduct generalized linear mixed modeling to assess for change in self-reported ART adherence from baseline to the six-month follow-up period and compare between arms. Generalized linear mixed modeling will be used to account for the effect of response clustering within participants. Models will adjust for the covariates specified above (section 4.4) and include random effects for dyad and intercept.

The model testing H3 is summarized as Equation H3:

$$\begin{aligned} \text{ART adherence} = & \text{Intercept} + B_1(\text{Arm}) + B_2(\text{Categorical variable corresponding to timepoint of adherence assessment; two degrees of freedom}) + \\ & B_3(\text{Arm * Timepoint of adherence assessment; two degrees of freedom}) + B_4(\text{Baseline adherence level}) + B_5(\text{Partner HIV status}) + B_6(\text{Respondent Age}) + B_7(\text{Respondent Sex}) + \text{Error} \\ & + \text{Random effects for the clustering within participant across timepoints and by dyad.} \end{aligned}$$

If the statistical test for the interaction between arm and timepoint is significant at the  $\alpha=0.05$  level, then we conclude that study arm significantly impacts the change in ART adherence. Within arm, adjusted estimates of changes in adherence will be presented along with 95% confidence intervals.

To test **hypothesis 4 (H4)**, we will conduct chi-square tests to assess for differences in uptake of OST between study arms. Adjustments for small sample sizes will be made as appropriate.

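### The only stated power, 80% at f=.15, comes from a repeated-measures ANOVA and is not the power of the SAP's primary t-test on EMD days, which neither document gives

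*Protocol*

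**What the plan says.** Protocol 4.6.12 holds the only power statement in either document: "With 30 dyads per arm, we would have 80% power to detect a medium effect size", given as f=.15 at alpha .05. It was obtained in G*Power "using a repeated measures within-between ANOVA approach". The section does not say which term of that ANOVA was used (between arms, time, or arm by time). It also does not give the outcome, the number of measurements, the correlation between them or any sphericity correction. Recruitment of 66 dyads, to leave 60 for analysis, rests on this figure.

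Elsewhere the protocol describes four assessments. Section 4.6 says "Participants in both arms will be assessed at 4 time points", section 4.6.5 says "There will be four main repeated assessment occasions", and section 4.2 has couples "assessed with repeated measures at four time-points on ART adherence". Section 4.6.5 makes EMD-measured adherence the primary adherence outcome, and section 4.7 tests the primary null hypothesis at two-sided .05.

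SAP 4.2 defines the primary dependent variable as "Number of days EMD is opened from baseline to six-month follow-up (0 to 180 days"), one value per participant. For hypothesis 1, SAP 4.5 says "we will conduct t-tests to assess for differences in ART adherence rates over six months (0 to 180 days) between study arms". The only arm-by-time analysis in the SAP is for hypothesis 3, a secondary outcome: "generalized linear mixed modeling to assess for change in self-reported ART adherence from baseline to the six-month follow-up period and compare between arms". The SAP gives no sample size or power statement.

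**The concern.** Power belongs to a particular test of a particular outcome. The figure that sizes this trial comes from a design with repeated measurements within each unit. The primary test has no repeated measurements and no time term: it compares two arm means of a single six-month total. The two tests respond differently to the correlation between occasions. A high correlation helps a within-unit contrast and hurts a comparison of arm averages, so the power of one cannot be carried over to the other.

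What is at stake is interpretation. Protocol 4.7 commits to a formal test of the primary null and also wants the pilot to inform power and detectable effects for a larger trial. A reader who attaches the 80% to the EMD comparison could give a non-significant result more weight than it deserves, or carry the figure into planning the next study.

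**Working it through.** **Inputs from the documents.** Power 80%, f=.15, alpha .05 and 30 dyads per arm, so N=60 (Protocol 4.6.12). Four occasions, m=4 (Protocol 4.2, 4.6, 4.6.5). Two arms, k=2. Two-sided testing (Protocol 4.7, SAP 4.1).

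**Inputs not in the documents.** Correlation between occasions ρ, and sphericity factor ε. I assume ρ=0.5 and ε=1 as a starting point and show a range.

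**Step 1: can the 80% be reproduced?** For the arm-by-time interaction, the noncentrality is λ = f²·N·m·ε/(1−ρ), with df (k−1)(m−1)ε and (N−k)(m−1)ε.

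With ρ=0.5 and ε=1: λ = 0.0225 × 60 × 4 / 0.5 = 10.80, df 3 and 174, power 78.6%. That is within two points of the stated figure.

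| Interaction, N=60, f=.15 | Power |
|---|---|
| m=4, ρ=0.3 | 63% |
| m=4, ρ=0.5 | 78.6% |
| m=4, ρ=0.516 | 80% |
| m=4, ρ=0.7 | 95% |
| m=4, ρ=0.5, ε=0.75 | 69% |
| m=3, ρ=0.5 | 71% |
| m=3, ρ=0.6 | 81% |

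So the figure is compatible with an interaction on four occasions, but it does not identify one. Three occasions at ρ=0.6 fit about as well. With two arms, the time effect has the same λ and df as the interaction. Taking 120 individuals at ρ=0 (m=4) gives 79%.

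**Step 2: could it be the between-arm term?** This is the term of the ANOVA closest to the SAP's t-test. Here λ = f²·N·m/(1+(m−1)ρ), with df 1 and N−2 = 58.

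- ρ=0: λ = 5.4/1 = 5.40, power 63%
- ρ=0.3: λ = 5.4/1.9 = 2.84, power 38%
- ρ=0.5: λ = 5.4/2.5 = 2.16, power 30%
- ρ=0.7: λ = 5.4/3.1 = 1.74, power 25%

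Power falls as ρ rises. With 60 units and four occasions it therefore does not reach 80% at any non-negative correlation.

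**Step 3: the primary t-test's own sensitivity.** Assume one index participant per dyad, n=30 per arm, df 58. The noncentrality is d·√(n/2) = d·√15, where d is the difference in SD units.

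- 80% power at d = 0.736, about 0.74 (0.70 with all 33 per arm)
- Expected 95% CI half-width: t(.975, 58)·√(2/30) = 2.002 × 0.258 = 0.517, about 0.52 SD

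The documents give no SD for the 0 to 180 day count, so neither figure can be turned into days.

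**Step 4: dependence on who is analysed.** SAP 3.2.2 gives EMDs to HIV-positive participants, and Protocol 4.4 allows partners to be HIV-positive. In the extreme case that every partner also contributes a count, n could be 60 per arm, and 80% power would need d of about 0.52 if all counts were independent. Counts within a dyad may be correlated, and a plain t-test makes no allowance for that.

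**The case against.** The strongest reply is that nothing in the protocol conflicts with itself. Section 4.6.12 attaches the 80% to no outcome and no t-test, and a repeated-measures calculation suits a protocol that assesses adherence repeatedly and defines EMD adherence over the past month (4.6.6). The gap opens only when the SAP makes the outcome a single six-month count. This is also a pilot aimed at safety, feasibility, acceptability and parameter estimation. Section 4.7 already promises 95% confidence intervals, which show imprecision directly, and SAP 3.1 describes randomisation as done. All of this stands. It lowers the severity and explains how the gap arose. It does not supply the missing figure.

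A second reply is that the arm-by-time reading is an inference. That stands too. Four occasions is even awkward for the EMD: the device is set up at the baseline visit or mailed after it (Protocol 4.6.1, 4.6.6), so there would be no past-month EMD value at baseline. The sponsor should be asked which term and inputs were used, not told.

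Three stronger readings are tempting, and the documents support none of them:

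- **The 80% is miscalculated.** Plausible inputs give close to 80%, so no error is shown. Because the inputs are unstated, the calculation cannot be confirmed as correct either.
- **Power fell from 80% to some much lower number.** That would set a chosen d against f=.15. The f of an interaction and the d of a t-test are different quantities, and the documents state no d for the EMD count.
- **The trial needs more dyads.** The pilot's aims do not require a given power for the EMD test.

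**Conclusion.** The point holds as a minor inconsistency. The stated 80% is not the power of the SAP's primary test, and neither document gives that power. This conclusion rests on the text alone and does not depend on which ANOVA term was used.

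The size rests on assumptions. With one index participant per dyad, 30 independent participants per arm and a two-sided .05 test, the primary comparison detects about 0.74 SD with 80% power and estimates the difference to within about ±0.52 SD. The SAP does not say that only index participants are analysed, so these figures are conditional. Enrolment and conduct are unaffected; what changes is how the primary result should be described and read.

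**What to change.** Text only, with no change to sample size.

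1. In the SAP and the report, say that the 80% in Protocol 4.6.12 does not apply to the primary EMD t-test. Retrieve the G*Power record and report the ANOVA term, number of measurements, correlation and sphericity correction actually used.
2. State the primary test's own sensitivity. Suggested wording: *If one index participant per dyad is analysed, 30 per arm gives the two-sided 0.05 t-test on EMD days 80% power at a standardised difference of about 0.74, with an expected 95% confidence interval half-width of about 0.52 SD.*
3. Say whether HIV-positive partners with EMDs enter the test. If they do, recompute the figure and use an analysis that allows for clustering within dyads.

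The cost is recovering the power inputs and a few sentences. If partners are included, there is also a change from a plain t-test to one that handles dyads.
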